### **Sample size calculation**

To determine the ideal number of participants, we have considered our first aim, which is to identify the variables linked to the CS phenotype that could help predict the response to treatment based on SMT for CLBP. In order to do this, we will perform a multiple regression analysis, using five independent variables as predictors, in particular the score on the pain catastrophizing scale (PCS) and central sensitization inventory (CSI) questionnaires (indicators of catastrophism and CS), the pressure pain thresholds (PPTs) in the primary pain area (marker of primary hyperalgesia), the urinary levels of the cytokine Tumor Necrosis Factor Alpha (TNF- $\alpha$ ; marker of inflammation) and finally the expectations of relief for each patient (indicative of potential placebo effects). The baseline values of these variables will be included in the multiple regression model. For each predictor variable, it is recommended to estimate about ten sample elements, therefore we predict that a sample size of 50 patients per group will be necessary (Ortega Calvo and Cayuela Dominguez, 2002). Taking into account two groups, one that will receive real SMT and the other placebo SMT, we will need a sample of 100 patients. An additional group of age and sex-matched healthy individuals without CLBP of the same size (50 participants) will be recruited to be used as a reference group, to determine

reference values in a healthy population for the predictor variables (questionnaires, PPTs, cytokines only)

Regarding the two main outcome variables (pain intensity and disability related to low back pain), we expect a reduction in pain and disability after one month in patients who receive 12 sessions of SMT compared to placebo. We aim to detect small to moderate effects since it is a one-month intervention in patients with chronic pain unresolved by other treatments over at least 3 months. Therefore, based on an effect size of  $f = 0.175$ , an alpha of 0.05, a power of 0.8 for 2 groups and 2 repeated measures (baseline and session 12), and a correlation between the repeated measures of 0.5, the size of the necessary sample is 34 patients per group and a total of 68 patients to detect statistically significant changes in clinical pain and disability. Therefore, our analysis based on the regression model to predict the clinical course provides us with a large enough size for both the first and second aims of this study.

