Official Title:

Efficacy of Chiropractic Spinal Manipulative Therapy in Patients With
Primary Chronic Low Back Pain: a Mechanistic Randomized Controlled
Trial

NCT number: Not Available

Unique Protocol ID: SMTCLBP

Date: December 15th, 2021

Statistical analyses

The normal distribution of the data will be verified using the Kolmogorov-Smirnov test. Data deviating from normality will be transformed to obtain a normal distribution before being entered into the data analysis. The two main outcome variables (clinical pain intensity and disability related to low back pain) will be compared between groups (SMT vs. placebo) over time (baseline and session 12) using a mixed analysis of variance. Average pain intensity since the previous treatment visit and in the seven days prior to the initial visit will be the variable used for statistical analyses. With an exploratory objective, the secondary variables (PCS, CSI, BDI-II, GAD scores, PPTs, degree of pain widespreadness, urinary cytokine levels, number and severity of reported adverse effects, presence of leg pain, pain medication use) will be compared between groups (SMT vs placebo) over time (baseline and session 12) using another mixed analysis of variance. To test a priori hypotheses, significant effects will be decomposed using planned comparisons. For the rest of the effects, Tukey's HSD will be used for testing any pair-wise comparisons between group means.

Pearson's product-moment correlation analyses will be carried out to examine the association between primary variables and secondary variables that demonstrate significant effects between groups over time. Subsequently, two multiple regression models will be used to examine the predictors of improvement in clinical pain and disability over time in patients who have received SMT, using secondary variables with a significant association with the primary variables. The secondary variables used for this analysis will be: baseline PCS and CSI score, baseline PPTs in the primary pain region, baseline TNF- α levels, and baseline expectations of pain relief. In addition, in another

regression model, the changes (delta) in these variables (except expectations of pain relief, since it is only measured at baseline) throughout the 4 weeks of treatment will be used as predictor variables. This is done to identify the variables most associated with clinical evolution, in order to answer the mechanistic question.

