In order to interpret the values obtained in patient groups, they will be compared with reference values obtained from the healthy controls to both CLBP groups. This will allow characterizing the patient groups to determine whether they show increased psychological symptoms, increased pain sensitivity and hyperalgesia as well as increased TNF-alpha levels compared with a reference healthy population. In order to do this, a series of mixed analyses of variance will be performed to examine differences in PPTs, urinary TNF- α levels, PCS, CSI, BDI-II and GAD scores before and after treatment between the three groups (control, SMT and placebo). To test a priori hypotheses, significant effects will be decomposed using planned comparisons. For the rest of the effects, Tukey's HSD will be used for testing any pair-wise comparisons between group means.

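### The SAP prescribes Tukey's HSD after before-and-after mixed ANOVAs without naming an error term; in its classical one-error form it cannot suit both between-arm and before-after comparisons of group-by-time means.

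*SAP*

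**What the plan says.** The SAP (Statistical analyses) analyses pain intensity and disability in a two-group, two-time model: they "will be compared between groups (SMT vs. placebo) over time (baseline and session 12) using a mixed analysis of variance". The secondary variables get the same type of model, with a stated exploratory aim. The SAP's closing paragraph, on healthy controls, extends the model to three groups: "a series of mixed analyses of variance will be performed to examine differences in PPTs" and in TNF-α and questionnaire scores.

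Both parts give the same follow-up rule. First, "To test a priori hypotheses, significant effects will be decomposed using planned comparisons". For the remaining effects, Tukey's "HSD will be used for testing any pair-wise comparisons between group means".

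Neither part states the error term, the degrees of freedom or the set of means that HSD will use. The planned comparisons are not listed either, so the boundary between the two routes is open.

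The Protocol (Sample size calculation) assumes "a correlation between the repeated measures of 0.5" and plans 50 participants in each of the three groups.

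**The concern.** In the two-by-two models, the group and time main effects each have two levels and need no pairwise procedure. HSD therefore has work to do only on the four group-by-time means. These mix independent pairs (SMT against placebo at one visit) with paired ones (before against after in one arm). Classical HSD assumes independent means with one common error variance and applies one critical difference to every pair. With correlated repeated measures, no single critical difference is right for both kinds.

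If the within-patient error is used, arms can be declared different when they are not. If the pooled or between-patient error is used, real changes within an arm are missed. The six means of the three-group models raise the same issue. At stake is which markers are reported as having changed or as differing between groups.

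**Working it through.** **Inputs.** From the Protocol, Sample size calculation: f = 0.175, alpha 0.05, power 0.8, 2 groups, 2 measures, ρ = 0.5, and n = 50 per group. The value ρ = 0.7 and the 0.5 SD improvement are assumptions of this check.

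**The plan's own figure.** For the group-by-time effect, λ = f²·N·m/(1−ρ) = 0.030625 × 68 × 2/0.5 = 8.33 on 1 and 66 df. Power is 0.812 at N = 68 and 0.7997 at N = 66, so the stated 68 reproduces. It does not depend on the follow-up method.

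**True variances** (cell variance s²):
- between arms at one visit: 2s²/n
- before-after within an arm: 2s²(1−ρ)/n

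At ρ = 0.5, n = 50 and s = 1, these are 0.04 and 0.02, a twofold difference. The standard errors are 0.200 and 0.141.

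**Candidate error terms.** Within-patient MS = s²(1−ρ) = 0.5; between-patient MS = s²(1+ρ) = 1.5; pooled MS = s² = 1.0. The ratio of the standard error used to the true one at ρ = 0.5 is:

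| Error term | Between-arm pair | Before-after pair |
|---|---|---|
| Within-patient | 0.71 | 1.00 |
| Pooled | 1.00 | 1.41 |
| Between-patient | 1.22 | 1.73 |

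At ρ = 0 all the ratios equal 1.

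**Hand check.** With q(4, 98) = 3.70, the within-patient critical difference is 3.70 × √(0.5/50) = 0.370. That is 0.370/0.200 = 1.85 true standard errors for a between-arm pair, or about 6% per pair. The intended multiple is 3.70/√2 = 2.62, or about 1%. The between-patient critical difference is 3.70 × √(1.5/50) = 0.641, larger than the 0.5 SD change to be detected.

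**Simulation A: only SMT improves, by 0.5 SD, and HSD is applied to four means after a significant interaction.** The gate opens often. The contrast in change has standard error √(2 × 2(1−ρ)/n) = √(2/50) = 0.2, so the signal is 0.5/0.2 = 2.5 standard errors and power is about 70%. Rates below are among trials that pass the gate; repeat runs agree to about one percentage point.

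| Result | ρ | Rate | Comparator |
|---|---|---|---|
| False baseline arm difference, within-patient error | 0.5 | about 6% | about 1% intended |
| Same | 0.7 | about 15% | about 1% intended |
| SMT change detected, pooled error | 0.5 | about 58% | 94% with the right error |
| SMT change detected, between-patient error | 0.5 | about 25% | 94% with the right error |

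**Simulation B: both arms improve by 0.5 SD, with the within-patient error.** A false between-arm claim at either visit occurs in 12% of trials (ρ = 0.5) or 24% (ρ = 0.7) if HSD is run regardless of the interaction. If a significant interaction is required first, it occurs in 2.4% or 3.0% of all trials. For six means the gated rates are 2.9% and 3.7%.

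**Where HSD is sound.** On the three group means averaged over time, with the between-patient MS, the simulated family error is 4.5% to 5.5%.

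**The case against.** The strongest reply is that the single error term is not in the SAP. A Tukey-type adjustment can be used with a standard error matched to each contrast, and then the fault disappears. This stands: the defect is that the plan leaves the choice open, not that it makes the wrong one. A reader might infer that one kind of comparison always gets the wrong error. The text does not support that, and at ρ = 0 the error terms coincide.

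Second, the rule concerns comparisons between group means, which may exclude before-after changes. If so, the lost power for change does not arise from this sentence. The false between-arm difference under the within-patient error still would.

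Third, the natural reading is that HSD follows only a significant effect. On that reading, false between-arm claims when the arms improve equally stay near 2% to 3%, and the 12% to 24% rates do not apply. This stands for that scenario, although the SAP attaches the significance condition to the planned comparisons and does not clearly repeat it for HSD. The gate does not help when a true interaction opens it, as Simulation A shows.

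Fourth, the reach is small. A priori hypotheses go to planned comparisons, and the benefit of SMT on pain and disability that the Protocol expects plausibly belongs there. The step that selects variables for correlation uses significant effects between groups over time, which is the interaction test. This also stands.

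**Conclusion.** The point holds as a cheap improvement to follow-ups that are not a priori. If HSD is applied in its classical form to group-by-time means, the choice of error term changes which follow-ups are significant, and by a material amount at the protocol's own correlation. After a true interaction, the rate of false baseline differences is about 6% instead of 1%, or detection of a real 0.5 SD change falls from about 94% to 58% or 25%. These sizes rest on normal data, equal variances, 50 per group, a 0.5 SD improvement in SMT only, and four means.

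Two stronger inferences are tempting and unsupported. One is that every follow-up outside the planned comparisons has a wrong significance level. Comparisons on the three-group main effect are correct, and so is any implementation with contrast-specific errors. The other is that the trial's main result is at risk. The interaction F test, the planned comparisons and the sample size are untouched.

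**What to change.** For group-by-time follow-ups in both parts of the SAP, replace Tukey's HSD with a short stated list of contrasts for each variable:
- between groups in change from baseline;
- between groups at session 12 (the 4-week visit for healthy controls);
- within-group change.

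Take each standard error from the fitted model for that contrast, and apply a multiplicity adjustment such as Holm across the list. Keep Tukey's HSD only for the three-group main effect in the comparison with healthy controls. Merely naming a contrast-matched error term would cure the standard-error fault; the list also shows which comparisons fall outside the a priori set.

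The cost is one SAP paragraph, with the same data and software. The downside is that some between-group follow-ups may be significant slightly less often.

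### The planned Pearson correlations have no arm term and no stated population or values; if both arms are pooled, arm differences alone can create or mask an association

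*SAP*

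**What the plan says.** The SAP, under Statistical analyses, sets out three linked steps.

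1. **Screen.** The secondary variables "will be compared between groups (SMT vs placebo) over time (baseline and session 12) using another mixed analysis of variance".
2. **Correlation.** "Pearson's product-moment correlation analyses will be carried out to examine the association between primary variables and secondary variables that demonstrate significant effects between groups over" the treatment period. No arm term, stratification or partial correlation is named. The sentence does not say whether both arms, SMT patients only, or each arm separately are used. Nor does it say whether baseline, session-12 or change values are correlated.
3. **Regression.** Next, "two multiple regression models will be used to examine the predictors of improvement in clinical pain and disability over time in patients who have received" real SMT. The restriction to SMT patients appears here, together with an entry description: "using secondary variables with a significant association with the primary variables". The SAP then lists the five baseline predictors by name.

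An arm difference is also expected in the primary variables. The Protocol, under Sample size calculation, says "we expect a reduction in pain and disability after one month in patients who receive 12 sessions of SMT compared to placebo".

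**The concern.** A correlation between a marker and pain or disability is meant to show that patients whose marker moved were the ones whose symptoms moved. A plain Pearson test in a pooled two-arm sample tests something else, namely zero total correlation, and that includes the part due to arm membership. If SMT shifts both variables, patients in one arm tend to have higher values of both and patients in the other arm lower values of both. A correlation follows even when nothing links the two variables within an arm.

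The plan makes this situation likely. Markers reach the correlation step because they differed by arm over time, and the trial is designed to find an arm difference in pain and disability. A significant pooled correlation could therefore restate what the analyses of variance have already tested, yet be read as evidence that the marker tracks clinical response. In a trial described as mechanistic, that reading matters. The opposite error is also possible: if the within-arm association runs against the direction of the arm shifts, the two partly cancel.

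**Working it through.** **Inputs**
- From the Protocol, Sample size calculation: "based on an effect size of $f = 0.175$ , an alpha of 0.05, a power of 0.8 for 2 groups and 2 repeated measures", a correlation of 0.5 between the repeated measures, 34 per group (68 in total) for this comparison, and 50 patients per group planned.
- Assumed: both arms pooled; change scores correlated; normal data; no within-arm correlation unless stated; and the arm shift in the marker, for which the documents give no figure.

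**Step 1. Reproduce the plan's sample size.** For the group-by-time effect, lambda = f² × N × m / (1 − rho), with m = 2 and rho = 0.5, on 1 and N − 2 degrees of freedom. Power is 0.7997 at N = 66 and 0.8116 at N = 68. The stated 68 (34 per group) is the first even N to reach 0.80, so it reproduces.

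**Step 2. Convert f to an arm difference in change.** lambda = 0.175² × 68 × 2 / 0.5 = 8.33. For a two-sample comparison of change, lambda = d² × 34 / 2 = 17d². So d² = 8.33 / 17 = 0.49 and d = 0.70 SD of change.

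**Step 3. Pooled correlation with none within arms.** With equal arms and shifts d1 and d2,

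r = (d1 × d2 / 4) / sqrt((1 + d1²/4)(1 + d2²/4)).

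- Both 0.70: 0.1225 / 1.1225 = 0.109.
- Both 0.35: 0.0306 / 1.0306 = 0.030.

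**Step 4. Rejection rate of the nominal 5% test.** Simulation with 50 per arm and 20,000 or 40,000 trials per setting. The marker is kept if its group-by-time test has p < 0.05 (a screened trial), and the correlation is then tested.

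| Shift in outcome (SD) | Shift in marker (SD) | Pooled Pearson, screened trials |
|---|---|---|
| 0 | 0.70 | 5% |
| 0.35 | 0.35 | 7% |
| 0.35 | 0.70 | 9% |
| 0.70 | 0.35 | 13% |
| 0.50 | 0.50 | 10% |
| 0.70 | 0.70 | 20% |
| 0.80 | 0.80 | 29% |
| 1.00 | 1.00 | 53% |

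The correlation adjusted for arm rejects in about 5% of screened trials throughout. The SMT-only correlation also stayed at about 5% wherever it was run. With both shifts at 0.70, pooled Pearson rejects in 19% of all trials and 20% of screened trials, so the screen adds little there. The inflation comes from the two shifts.

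**Step 5. Masking.** Take a within-arm correlation of −0.3 with both shifts at +0.70. The pooled correlation becomes (−0.3 + 0.1225) / 1.1225 = −0.158. In simulation, pooled Pearson detects the association in about 34% of trials and the arm-adjusted correlation in 86%.

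**The case against.** **Pooling is not stated.** The correlations lead into models fitted in SMT patients, so an SMT-only analysis is not excluded. With SMT-only or per-arm correlations the artefact disappears, and baseline values are balanced by randomisation. This stands, and the point is conditional on it. Pooling is still the more natural reading, because the screen compares the two arms and the SMT restriction is attached only to the later step.

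**The 0.70 SD figure is the plan's for pain and disability only.** This also stands. The Protocol gives no effect size for any marker and describes the effects it seeks as small to moderate. The rows at 0.80 and 1.00 SD show sensitivity and are not expectations. Even at 0.70 SD the spurious r of about 0.11 is roughly 1% of variance.

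**A reader might infer that false correlations decide which variables enter the regressions.** The entry description invites this, but the documents do not support it. The SAP names the predictors, and the Protocol fixes the same five in advance and sizes the regression on them. Expectations of relief are measured only at baseline and are not in the screened list. They could not pass a test of change between groups, yet they are in the model. The outcome models are fitted in SMT patients, where a between-arm artefact cannot arise. The model of changes uses the same named variables apart from expectations. Its sentence does not repeat the population, but it follows directly from the SMT-only models.

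**The step is exploratory.** The SAP gives the secondary comparisons an exploratory objective, and the primary SMT-versus-placebo comparison is untouched. This limits the consequences but does not make the pooled test answer the question asked of it.

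**Conclusion.** The concern holds conditionally. If the correlations pool both arms on change or session-12 values, and both variables truly differ by arm, the plain Pearson test does not test patient-level association. Its false-positive rate is about 20% with both shifts at 0.70 SD, about 7% to 13% with one or both at 0.35 SD, and the nominal 5% if the outcome does not differ by arm. It can also lose most of its power against an association of opposite sign.

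The harm falls mainly on the reported exploratory correlations and on any claim of significant association drawn from them. It would go too far to say that the SAP prescribes a pooled analysis, that the regressions are invalidated, or that 20% is the plan's own error rate. The SAP is silent on population and values, and the marker shift is an assumption. The change is worth making before analysis, but it does not affect the primary comparison.

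**What to change.** In the SAP's correlation sentence, state which patients and which values are used. If both arms are pooled, replace the plain Pearson correlation with a correlation of change scores adjusted for randomised arm. This can be a partial Pearson correlation given arm, or the coefficient of the marker in: change in outcome ~ arm + change in marker. Show the SMT-only and placebo-only correlations beside it, and base any statement of significant association on the arm-adjusted estimate.

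The cost is a short wording change and one degree of freedom per test. No new data or patients are needed.

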#### *Questionnaires variables*

The PCS and central CSI questionnaires will be completed before the beginning and upon completion of the study (Cuesta-Vargas et al., 2016; Garcia Campayo et al., 2008). Both these variables will be introduced as predictors in the regression model, due to their intrinsic association with a CS phenotype. The PCS will be used to identify specific pain cognitions that are usually present in patients with a CS phenotype, this measure will be used to evaluate the association of CLBP with psychosocial factors described by Smart et al. (Smart, et al., 2012). The CSI is an excellent tool to identify patients compatible with CS mechanisms, particularly when using the cut-off value of 40/100 (Scerbo et al., 2018). Pre and post reference values of these questionnaires will be taken from the healthy population sample in the same time-frame.

In addition, the Beck Depression Inventory II (BDI-II) and the Generalized Anxiety Disorder scale (GAD) questionnaires will be used to screen and quantify symptoms of depression and anxiety (García-Campayo et al., 2010; Sanz et al., 2005). The scores in these questionnaires will be measured both at baseline and follow-up for exploratory purposes and to determine whether significant correlations exist between any of these variables and the primary outcomes of pain and disability.

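### The SAP correlates BDI-II and GAD with pain and disability only if they first show a significant SMT-versus-placebo effect, a condition that the protocol does not set

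*SAP*

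**What the plan says.** The protocol (Questionnaires variables) has BDI-II and GAD scored twice, at the start and at follow-up. It calls this exploratory and names a further aim: "to determine whether significant correlations exist between any of these variables and the primary outcomes of pain and disability". It sets no precondition for looking at those correlations.

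The SAP (Statistical analyses) counts both scores among the secondary variables: "the secondary variables (PCS, CSI, BDI-II, GAD scores, PPTs, degree of pain widespreadness" and others. With an exploratory objective, these variables "will be compared between groups (SMT vs placebo) over time (baseline and session 12) using another mixed analysis of variance". The next paragraph plans Pearson correlations to "examine the association between primary variables and secondary variables that demonstrate significant effects between groups over time".

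No other text plans an unconditional correlation for BDI-II or GAD. The predictors that the SAP names for its regressions are PCS, CSI, PPTs in the primary pain region, TNF-α and expectations of relief. The three-group comparison with healthy volunteers uses BDI-II and GAD, but only to compare group means.

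**The concern.** The two documents disagree on when the BDI-II and GAD correlations are run: always under the protocol, only after a significant result under the SAP.

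The SAP's condition also does not serve the stated purpose. The screen asks whether the arms differ in how a score changes. The correlation asks whether patients with more depression or anxiety, or more improvement in them, have more pain and disability, or more improvement in those. A score that improves in step with pain equally in both arms fails the screen, although its correlation with pain may be strong. In a trial described as mechanistic, that is a result the investigators would want to see. Followed literally, the SAP omits it.

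**Working it through.** **Inputs.** From the protocol (Sample size calculation): 2 groups, 2 repeated measures, alpha 0.05, power 0.8, f = 0.175, "a correlation between the repeated measures of 0.5", and 100 patients planned in two groups of 50. The f of 0.175 is for pain and disability. Neither document gives an expected effect of SMT on BDI-II or GAD, so the effects below are an assumed range. Full data from 50 per arm are also assumed.

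**Reading of the screen.** It is taken as the SMT-versus-placebo group-by-time effect in the mixed analysis of variance. The SAP does not use the word interaction, but its preceding paragraph describes exactly that comparison in nearly the same words.

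**Step 1: reproduce the plan's own figure.** For the group-by-time interaction, λ = f² × N × m / (1 − ρ), with 1 and N − 2 degrees of freedom. At N = 68, λ = 0.175² × 68 × 2 / 0.5 = 8.33, and power is 0.812. At N = 66 it is 0.7997, just short of 0.80. The smallest even N is therefore 68, which agrees with the protocol: "the size of the necessary sample is 34 patients per group and a total of 68 patients". The same formula can then be used for the screen.

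**Step 2: put f on the scale of change.** With m = 2 and ρ = 0.5, λ = 4f²N. A two-sample t-test on change with difference d (in SDs of change) has λ = Nd²/4. Equating the two gives d = 4f, so f = 0.175 corresponds to d = 0.7.

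**Step 3: chance that a score passes the screen at N = 100.**

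| True arm difference in change (SD) | f | λ | Screen passed | Correlation not run |
|---|---|---|---|---|
| 0 | 0 | 0 | 5% | 95% |
| 0.3 | 0.075 | 2.25 | 32% | 68% |
| 0.5 | 0.125 | 6.25 | 70% | 30% |
| 0.7 | 0.175 | 12.25 | 93% | 7% |

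These figures are for one score. Without the condition, the last column is 0% throughout.

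**Step 4: what is lost when the correlation is not run.** Using Fisher's z, with atanh(r) × √(n − 3) compared with 1.96, power to detect r = 0.3 is 0.86 at n = 100 (0.3095 × 9.849 = 3.05) and 0.56 at n = 50. For r = 0.4 it is 0.99 and 0.83. The trial can therefore detect a moderate correlation.

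A simulation with 50 per arm, a true within-arm correlation of 0.4 and the test done in the SMT arm found a significant correlation in about 83% of trials with no screen. With the screen, this fell to 4%, 14%, 41% and 77% for arm differences of 0, 0.2, 0.4 and 0.7 SD. These are close to the pass rate times 83% (for example 0.05 × 0.83 = 0.04), so the loss comes from the screen and not from any weakness of the correlation.

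**The case against.** Four arguments can be made on the other side.

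- **The screen may seldom bite.** If SMT moves BDI-II and GAD as much as the plan assumes for pain and disability, the correlation is skipped in only 7% of trials. This stands. A smaller effect on mood scores is plausible but undocumented, so a reader should not infer that the analysis will usually be lost.
- **The analyses are exploratory in both documents.** Neither score is a primary outcome or a named regression predictor. This stands and keeps the severity low, but it does not remove the disagreement.
- **The SAP does not forbid extra correlations.** True, but a correlation run outside its stated rule would be unplanned, although the protocol gives it as a reason for collecting the data.
- **Ungated testing means more tests.** Also true. The protocol's promise covers only BDI-II and GAD, so an exemption for those two is enough, with exploratory labelling.

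A reader might also infer that the screen inflates the correlations that survive it, because a variable that passes has shifted between arms. The documents do not support this. Suppose the within-arm correlation is zero, the arms differ by 0.7 SD on pain and 0.5 SD on the score, and the arms are pooled unadjusted. The expected correlation is then (0.7 × 0.5 / 4) / √[(1 + 0.7²/4)(1 + 0.5²/4)] = 0.0875 / 1.092 = 0.08 before any screen. In simulation the pooled correlation is significant in 12.6% of trials without the screen and 15.3% with it. In the SMT arm alone, or adjusted for arm, the rate is about 5%. Pooling causes nearly all of the inflation, and the SAP does not say that the arms are pooled.

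**Conclusion.** The mismatch is real. The protocol promises BDI-II and GAD correlations without condition. The SAP makes them depend on a significant between-arm effect, which answers a different question, and no other text restores them.

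The size runs from 95% of trials with the correlation not run (no SMT effect on the score) to 7% (an effect as large as that planned for pain and disability), with 68% and 30% at 0.3 and 0.5 SD. It rests on 50 patients per arm with full data, two-sided 0.05, the group-by-time reading of the screen, and an assumed range of effects.

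The point is minor. It concerns exploratory analyses, and no primary comparison changes. It does not show that the correlations will usually be suppressed, nor that those retained are biased by the screen.

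**What to change.** In the SAP (Statistical analyses, correlation paragraph), delete the clause that limits the correlations to variables with a significant between-group effect over time, at least for BDI-II and GAD. State instead that both scores will be correlated with pain and disability whatever the analysis of variance shows:

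- at baseline, and as change from baseline to session 12, because the protocol does not limit its question to change;
- in all patients, adjusted for arm (a partial correlation), so that a shared arm effect cannot pass for an association;
- labelled exploratory.

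If the sponsor does want the condition, the protocol's Questionnaires variables section should state it, so that the two documents agree. That removes the contradiction but keeps a screen that does not fit the question.

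The cost is a change of wording and a few more exploratory correlations to report. It needs no new data, visits or patients.
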